### 7.1.2 PRNT

Details on the PRNT procedure can be found in SOP BN0003536: “Human Plaque Reduction Neutralization Test Using Vaccinia Virus Western Reserve”.

The PRNT GMT is calculated by taking the antilogarithm of the mean of the log10 titer transformations. Titers below the detection limit are assigned the arbitrary value of 1.

The seroconversion rate is defined as the percentage of seroconverted subjects based on the total number of subjects included. Seroconversion is defined for initially seronegative subjects as appearance of antibody titers  $\geq$  detection limit. For subjects who are initially seropositive (i.e. with baseline [V1] antibody titers  $\geq$  detection limit) at least a doubling of the titer is needed to fulfill the definition of seroconversion.

## 7.2 Future Use of Lab Specimen

Serum remaining after completion of all immunogenicity testing for the trial will be stored for future analysis supporting the licensure path of MVA-BN® smallpox vaccine. Future analysis will facilitate the bridging of trial results to animal immunogenicity results and/or to immune response data collected from subjects vaccinated with traditional smallpox vaccines. Subjects will be asked to consent to storage / future use of samples and will be informed about data protection measures. Specimens will be stored in BN's secured laboratory area or at an external storage facility in a coded, anonymized manner to ensure data protection. Genetic testing will not be performed.

## 8 Safety and Reactogenicity

Safety will be monitored by performing physical examinations including vital signs, routine laboratory measurements as well as by evaluating local and general solicited AEs and unsolicited AEs.

Using replication-competent vaccinia-based smallpox vaccines during smallpox vaccination programs in the US during the last years, cases of acute myocarditis and pericarditis were observed ([Cassimatis, 2004](#)). No confirmed cases of myo- or pericarditis have been observed for MVA-BN® smallpox vaccine. However, as a precautionary measure, special cardiac monitoring assessments will be performed.

### 8.1 Definitions

#### 8.1.1 Medical History

Symptoms present before or at the screening visit will be documented in the medical history.

#### 8.1.2 AEs

Any new signs, symptoms or changes in health starting after ICF signature are documented in the AE section of the eCRF. AEs are recorded based on unsolicited and solicited questioning ([Section 8.1.2.1](#) and [8.1.2.2](#)).

##### 8.1.2.1 Unsolicited AEs

Unsolicited AEs are defined as any untoward (undesirable) occurrence of a medical event in a clinical trial subject temporally associated with the administration of an IMP or a medical product (MP) which does not necessarily have a causal relationship with this IMP/MP. For Group 1 and 2 up to Visit 5 (Week 8) and for Group 3 up to Visit 8 (Week 16) all AEs (e.g. feeling of ill-health, subjective symptoms and objective signs, intercurrent diseases, accidents, etc.) observed by the investigator and/or reported by the subject must be recorded in the eCRF regardless of the assessment of causality in relationship with the IMP/MP.

Abnormal laboratory values assessed as being clinically significant by the investigator are to be documented as AEs. In addition, abnormal laboratory values fulfilling the Grade 3 or Grade 4 criterion according to the toxicity scale ([Section 16.1](#); [Appendix I: Toxicity Scale for Laboratory Values](#)) are to be documented as AE in the eCRF, regardless of whether they are considered clinically relevant or not. For lab values fulfilling the Grade 3 or 4 criterion, the decision to repeat the labs is left at the discretion of the PI. Toxicity grade and seriousness of an AE will be assessed separately, i.e. a Grade 3 or Grade 4 AE will not automatically be regarded as serious.

The investigator should ask the subject if they have experienced any AEs since their last visit. All intercurrent diseases reported by the subject, need to be recorded by the investigator in the appropriate section of the eCRF.

### **8.1.2.2 Solicited AEs**

Within this clinical trial protocol solicited AEs are defined as all symptoms specifically listed in the memory aid provided to the subjects following each vaccination. The subjects are requested to monitor and record local symptoms (i.e. erythema, swelling, induration, pruritus and pain at the injection site) as well as general symptoms (i.e. body temperature, headache, chills, myalgia, nausea and fatigue) in the memory aid daily for the day of vaccination and the following seven days (Days 0-7, 8 day period).

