**If the subject is still eligible for participation in this trial the subject will be randomized.**

#### **The following tasks will be performed after randomization:**

- Administration of first MVA-BN® vaccination
- Subject observation by CTS staff for at least 30 minutes after vaccination
- Recording of immediate AEs/AESIs/SAEs
- Handout of memory aid for first vaccination, ruler and thermometer

Temporary deferral of vaccination: If an acute illness is present the subject may be vaccinated at a later date within the accepted time window. The vaccine can be administered to persons with a minor illness such as diarrhea, mild upper respiratory infection, or any other mild condition with or without low-grade febrile illness, i.e. oral temperature < 100.4°F (< 38.0°C).

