### 8.2.6 Solicited AEs

After each vaccination subjects receive a memory aid to record solicited local and general AEs most likely to occur on the day of vaccination and the following seven days (Days 0-7; 8-day period).

All solicited symptoms observed after vaccination with details concerning the intensity and the course of the reaction should be documented there. The investigator will collect this information during the following scheduled visits and transfer it to the eCRF and the subject's medical record. Local and general reactions still ongoing after seven days will be measured or examined each day until resolution or until no further change can reasonably be expected, and the last day of symptoms and maximum intensity will be documented in the memory aid.

In case of severe and unexpected local and/or general reactions, the subject should be instructed to contact the trial physician outside of scheduled trial visits.

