### Treatment Emergent Adverse Event

An adverse event (AE) with onset either on the day of a vaccination, but after injection, or within the 28 days following injection. AEs recorded outside the 28 day window after the last injection of trial vaccine will be classified as non-treatment emergent AEs.

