### 3.3.3 General Considerations for AEs

MedDRA version 17.1 will be used for coding of AEs.

Duration of an AE is calculated as follows:

Unsolicited AE: expressed in [days]

- End date of AE – start date of AE + 1
- In case of (partially) missing start date or (partially) missing end date imputed dates will be used in the calculation.
- In case the AE is ongoing at the end date of the AE, the duration will not be calculated

Solicited AEs: expressed in [days]

end date of AE – start date of AE + 1

where

end date is the last day the symptom is defined as an AE

start date is the first day symptom is defined as an AE

(no matter if the AE occurred at every day between first day and last day).

- In case the AE is ongoing at the end date of the AE, the duration will not be calculated

Time interval between vaccination and start of AE are calculated as follows:

Relative day of start of AE is calculated as follows:

Unsolicited AEs: expressed in [days]

- Start date of AE – corresponding vaccination date
- In case of (partially) missing start date no calculation will be done.

Solicited AEs: expressed in [days]

- Start date of AE – corresponding vaccination date
- Where start date is the first day a symptom is defined as an AE, and vaccination day corresponds to Day 0.

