#### Solicited General AEs

Solicited general AEs will be summarized in the same manner as solicited local AEs.

In addition a similar summary table will be produced for relationship of the AEs to trial vaccine. Also the incidences of AEs with reasonable possibility of vaccine contribution (i.e. relationship to vaccine documented as “possible”, “probable”, “definite” or missing), and those with Grade  $\geq 3$  and with reasonable possibility of vaccine contribution will be summarized per vaccination period and overall by subject.

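### A general symptom already present before an injection can be counted as a solicited AE of that dose, because no rule in the plan compares it with the pre-dose state

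*Protocol*

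**What the plan says.** **Collection (Protocol).** Section 8.1.2.2 states that "solicited AEs are defined as all symptoms specifically listed in the memory aid provided to the subjects following each vaccination", with daily entries on Days 0-7. The general symptoms are body temperature, headache, chills, myalgia, nausea and fatigue. Section 8.2.6 adds: "All solicited symptoms observed after vaccination with details concerning the intensity and the course of the reaction should be documented there". The Visit 1 task list places "Handout of memory aid for first vaccination, ruler and thermometer" after vaccination and the observation period; the Visit 3 and Visit 6 lists use the same order. Before each injection the site takes vital signs and records AEs. Acute disease at vaccination is an exclusion, but the deferral notes at Visits 1, 3 and 6 permit vaccination during a minor illness.

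**Definitions that require something new.** Protocol 8.1.2, which covers solicited and unsolicited events, says: "Any new signs, symptoms or changes in health starting after ICF signature are documented in the AE section of the eCRF". Protocol 8.1.1 says: "Symptoms present before or at the screening visit will be documented in the medical history". The SAP defines a treatment-emergent AE as "An adverse event (AE) with onset either on the day of a vaccination, but after injection, or within the 28 days following injection".

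**Dating and counting (SAP).** In 3.3.3, for a solicited AE, "start date is the first day symptom is defined as an AE". In 3.3.2, an AE dated to a vaccination day but lacking a start time is assigned to that vaccination and regarded as treatment-emergent. In 3.5.9, incidence is the number of subjects developing the event in the 8-day window divided by the number who received that vaccination. This is written for local AEs, and then "Solicited general AEs will be summarized in the same manner as solicited local AEs". Related-only summaries are added, based on the investigator's causality rating (Protocol 8.2.6.2).

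**The concern.** The solicited definition rests on a symptom being on the list, not on when it began. The aid starts after the injection, so on the documents' description it holds no pre-dose entry to compare with. Symptoms such as fatigue, headache, nausea and myalgia can be present for reasons unrelated to the vaccine.

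Solicited general AEs are a named secondary safety endpoint, and the trial asks whether the larger regimens are tolerated as well as the standard one. Without a placebo group, nothing in the trial estimates the background. Any background counted as reaction therefore goes straight into the reported reactogenicity. It also affects comparisons between groups, in a direction that depends on the comparison.

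**Working it through.** **1. The plan's own safety figure.** Protocol 9.2 says 30 subjects per group give at least 95% probability of seeing an AE of incidence 1 in 10. Check: 1 - 0.9^30 = 0.958. It reproduces, and this point does not change it.

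**2. One case followed through the text.** A subject develops fatigue after Visit 2 and still has it at Visit 3.
- Protocol 8.1.2: it counts as new, because the reference point is consent and not the next injection. It is recorded as an AE before the second dose.
- Protocol 8.1.2.2: the subject enters fatigue on Day 0 of the second memory aid. It is a listed symptom, so it meets the definition.
- SAP 3.3.3: the start date can be read as Day 0.
- SAP 3.3.2: if the daily entry carries no clock time, the event is treatment-emergent and belongs to the second vaccination.
- SAP treatment-emergent definition: on true onset, the event should not count for this dose.

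The last two steps disagree, and no rule links the pre-dose record to the memory-aid entry. The reading that counts the event and the reading that rejects it are both available.

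**3. Pre-dose values.** Oral temperature is measured before each injection with the vital signs (Protocol 8.2.4 and the visit lists). No pre-dose grade is described for headache, myalgia, nausea, fatigue or chills.

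**4. Group 2 against Group 1, per dose.** Let p be the rate of true reactions and b the share of subjects whose pre-existing symptom is counted. Assume b is equal in the randomized groups and independent of reaction. Then observed rate = p + (1-p)b, and the observed risk difference = (1-b) × the true difference. The documents give neither p nor b. The illustration assumes true rates of 20% and 50%.

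| b | Group 1 | Group 2 | Difference (points) | Risk ratio |
|---|---|---|---|---|
| 0 | 20.0% | 50.0% | 30.0 | 2.50 |
| 5% | 24.0% | 52.5% | 28.5 | 2.19 |
| 10% | 28.0% | 55.0% | 27.0 | 1.96 |
| 20% | 36.0% | 60.0% | 24.0 | 1.67 |
| 30% | 44.0% | 65.0% | 21.0 | 1.48 |

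When the event is rarer, the risk ratio suffers more. For assumed true rates of 5% and 15% (ratio 3.0), b = 10%, 20% and 30% give 14.5/23.5%, 24/32% and 33.5/40.5%, so ratios of 1.6, 1.3 and 1.2.

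**5. Group 3 against a two-dose group, per subject.** Group 3 has three 8-day windows and Groups 1 and 2 have two. A persistent symptom adds the same share to each group. An intermittent one, with independent chance b per window and no true reaction, gives 1-(1-b)^3 against 1-(1-b)^2. The excess is b(1-b)^2.

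| b per window | Two windows | Three windows | False excess (points) |
|---|---|---|---|
| 5% | 9.8% | 14.3% | 4.5 |
| 10% | 19.0% | 27.1% | 8.1 |
| 20% | 36.0% | 48.8% | 12.8 |
| 30% | 51.0% | 65.7% | 14.7 |

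**The case against.** The strongest reply is that the plan already asks for new events, so the gap is only one of wording. Protocol 8.1.2 governs 8.1.2.2. Symptoms present at screening go to medical history, and AEs are recorded before each dose. The memory aid is reviewed with the subject, and reactions lasting beyond Day 7 are followed, so a symptom carried over from one dose has a documented course. The SAP speaks of onset, of events beginning in the window and of subjects developing them. Investigator causality gives a related-only view, and the intensity tables separate mild from severe events. The memory aid and eCRF instructions are not part of the two documents and may contain a pre-dose instruction.

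Much of this stands. A reader might infer from 8.1.2.2 that the plan has no check at all, or that every pre-existing symptom is counted after every dose. The documents support neither; counting is a possible reading, not a stated rule.

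The reply does not close the gap. The word new in 8.1.2 is anchored to consent, not to each injection. The missing-time rule in SAP 3.3.2 bypasses the onset requirement on Day 0. Causality is an open-label judgement, and a missing rating counts as related. The related-only results also leave the main tables unchanged, and the index lists no separate related-only table for solicited general AEs, only listings and pooled per-subject tables.

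Two further objections are fair. First, the effect is modest against sampling error. At 20% against 50% with 30 per group, the 95% half-width is 1.96 × √[(0.2×0.8 + 0.5×0.5)/30] = 0.229, about 23 points, while the shift in the difference is 1.5 to 9 points. The shift is systematic, however, and so is the rise in absolute rates. Second, dropping every same-term event that was ongoing at injection would also discard true worsening, so a remedy must keep grade increases.

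**Conclusion.** The point holds as an unresolved conflict between definitions. Protocol 8.1.2.2 and SAP 3.3.2 let a pre-existing general symptom count as a solicited AE of the next dose; Protocol 8.1.2 and the SAP's treatment-emergent definition point the other way. The existing checks are not applied to the main incidence, intensity and duration tables.

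A reader might infer that background symptoms dilute every regimen comparison. They do not. Shrinkage by (1-b) applies to Group 2 against Group 1 per dose, if b is equal across groups and independent of reaction. For Group 3 per-subject rates, intermittent symptoms push the other way because there are more windows.

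Every size given here rests on assumed values of b and p. Safety is compared descriptively, with no test or margin, so no formal conclusion turns on this. What is at risk is the accuracy of the reported rates for a secondary endpoint.

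**What to change.** **SAP 3.3.2 and 3.3.3.** State one rule that reconciles the solicited definition, the treatment-emergent definition and the missing-time rule: a solicited general AE is flagged as new only if the symptom was absent before that injection or its grade rose above the pre-dose grade. Base the flag on medical history and on AEs recorded as ongoing at Visits 1, 3 and 6. For temperature, use the pre-dose vital sign.

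**Data collection.** Where vaccination visits remain, add a short pre-injection grade (0-3) for headache, myalgia, nausea, chills and fatigue.

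**Tables 15.3.1.3.1 to 15.3.1.3.4.** Show incidence and maximum intensity for new-or-worsened events beside the existing all-events results. Give per-vaccination rates whenever Group 3 is compared with the two-dose groups.

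**Cost.** One SAP rule, one extra column, and about a minute per vaccination visit for the pre-dose grade. If only existing data are used, the flag is as good as the recording of ongoing symptoms. Protocol 8.2.1 directs medical history mainly to important diseases, so mild headache or fatigue may be missed. Keeping the all-events column means nothing is lost.

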### **8.1.2.3 AESIs**

An AESI is defined in this trial as:

- Any cardiac sign or symptom developed since the first vaccination
- ECG changes determined to be clinically significant
- Cardiac enzyme troponin I  $\geq 2 \times$  ULN

### **8.1.2.4 SAEs**

A SAE is any untoward medical occurrence that at any dose:

- Results in death
- Is life-threatening
- The term "life-threatening" in the definition of "serious" refers to an event in which the patient was at risk of death at the time of the event; it does not refer to an event which hypothetically might have caused death, if it were more severe.
- Requires in-patient hospitalization or prolongation of existing hospitalization
- Results in persistent or significant disability or incapacity
- Results in a congenital anomaly or birth defect
- or is an otherwise important medical event, e.g. leads to suspicion of transmission of an infectious agent

Medical and scientific judgment should be exercised in deciding whether expedited reporting is appropriate in other situations, such as important medical events that may not be immediately life-threatening or result in death or hospitalization but may jeopardize the subject or may require intervention to prevent one of the other outcomes listed in the definition above. These should also usually be considered serious.

Examples of such events are intensive treatment in an emergency room or at home for allergic bronchospasm; blood dyscrasias or convulsions that do not result in hospitalization; or development of drug dependency or drug abuse.

## **8.2 Assessment**

### **8.2.1 Relevant Medical History**

Relevant medical history will be documented at SCR and will focus particularly on any important diseases and in case of infections or tumors, the pathogen involved or the pathological diagnosis, if available. Special attention should be given to history of prior allergic reactions, especially to vaccines.

Diagnosis of HIV and disease state has to be documented separately: date of diagnosis, nadir, CD4 count and highest viral load up to six months before SCR.

In addition, smallpox vaccination history must be checked (check for a smallpox vaccination scar and any documentation of previous smallpox vaccination, if available; Note: check also for smallpox vaccination programs during military service or for smallpox response teams or history of vaccination with a poxvirus-based vaccine e.g. in the course of a clinical trial).

### **8.2.2 Prior and Concomitant Medications**

All concomitant (ongoing) medication except homeopathic substances and dietary supplements must be recorded in the eCRF and the subject's medical record including information about the indication, dosage regimen, and the onset and end of treatment.

The following medication, taken within three months prior to screening, will also be recorded in the eCRF and the subjects medical record: vaccines, corticosteroids (via any route of administration), other immune-modulating drugs, immunoglobulin and/or any blood products, investigational drugs and depot preparations which are still active at the date of SCR.

The antiretroviral medications, taken within six months prior to SCR, will also be recorded in the eCRF and the subject's medical record.

### **8.2.3 Physical Examination**

#### Complete physical examination

A complete physical examination will be performed at the SCR. The examination includes a review of major organ systems as well as height and weight. The examination should be directed at finding evidence of any infections, tumors and lymphadenopathy (a grading scale for lymphadenopathy is included in [Section 16.4; Appendix IV: Grading Scale for Lymphadenopathy](#)). In addition, auscultation of the heart and lungs to check specifically for signs of any heart condition will be performed.

#### Targeted physical examination

A targeted physical examination, guided by any signs or symptoms previously identified or any new symptoms that the subject has experienced since the last visit, is required at all visits starting at Visit 1. In addition, auscultation of the heart and lungs will be performed.

### **8.2.4 Vital Signs**

Blood pressure and pulse rate will be taken after the subject has been sitting for approximately two minutes. Body temperature will be measured orally.

### **8.2.5 Unsolicited AEs**

All intercurrent diseases reported when the investigator actively inquires the subject will be documented in the source and all required details (e.g. start and stop date, severity) will be assessed. Unsolicited AEs will be reported in the respective section of the eCRF and the subject's medical record.

AEs for Group 1 and 2 will be assessed and documented at all visits except FU 1 and FU 2 (i.e. Screening to Visit 5) and if ongoing at Visit 5, followed until resolution or until the FU 2 at the latest.

AEs for Group 3 will be assessed and documented at all visits except FU 1 and FU 2 (i.e. Screening to Visit 8) and if ongoing at Visit 8, followed until resolution or until the FU 2 at the latest.

SAEs/AESIs will be assessed and documented at all trial visits, including the FU 1 and FU 2. Ongoing AESIs which occurred after at least one vaccination will be followed up until resolution or achievement of stable clinical conditions. SAEs will be followed up until resolution or achievement of stable clinical conditions.

---

### Assessment of Intensity

For all unsolicited AEs not represented in the toxicity scale for Laboratory Values ([Section 16.1; Appendix I: Toxicity Scale for Laboratory Values](#)), the maximum intensity will be based on the following descriptions:

- Grade 1     An AE which is easily tolerated by the subject, causing minimal discomfort and not interfering with daily activities.
- Grade 2     An AE which is sufficiently discomforting to interfere with daily activities.
- Grade 3     An AE which prevents daily activities. (Such an AE would, for example, prevent attendance at work and would necessitate the administration of corrective therapy.)

